6.8 Safeguarding

At time points T1 and T2, we will follow the following plan to assess and manage risk:

The Greater Manchester Safeguarding Partnership is a cooperative partnership of the 10 Local Safeguarding Boards of Greater Manchester. Each of the 10 Local Authorities across the city have a nominated member on the Greater Manchester Safeguarding Partnership. If there are safeguarding concerns about any children in the study, the CI will be notified and will contact the appropriate safeguarding team for that child's place of residence, which will usually be the First Response team. However, if a member of the team is concerned about an immediate risk to a child, the Emergency Duty Team will be called. A list of phone numbers for the First Response teams and Emergency Duty Teams across the ten boroughs will be held by the CI, Co-CI, RA, and MHPs.

7. Definition of end of study

The intervention period is due to end by 31st January 2026, data collection is due to complete by 31st March 2026, and the study will close on 31st March 2027.

8. Ethical and regulatory considerations

8.1 Approvals

Before the start of the intervention period, a favourable opinion will be sought from an NHS Research Ethics Committee (REC) for the study protocol, informed assent forms (children aged 15-years-old and younger) consent forms (participants 16years-old and over) and other relevant study documents. All components of the research

involving data collection from research participants will commence following satisfactory NHS Ethics and HRA approval, as well as local Capacity and Capability approval from participating NHS Trusts. The study will be conducted in full conformance with all relevant legal requirements and the principles of the Declaration of Helsinki, Good Clinical Practice (GCP) and the UK Policy Framework for Health and Social Care Research 2017.

8.2 Regulatory Review & Compliance

Before any site can enrol patients into the study, the CI or designee will ensure that appropriate approvals from participating organisations are in place. Specific arrangements on how to gain approval from participating organisations are in place and comply with the relevant guidance.

For any amendment to the study, the CI or designee, in agreement with the Sponsor, will submit information to the appropriate body (REC, HRA, Sponsor and participating sites) for them to issue approval for the amendment. The CI or designee will work with sites (R&D departments at NHS sites as well as the study delivery team) so they can put the necessary arrangements in place to implement the amendment to confirm their support for the study as amended.

All correspondence with the REC and HRA will be saved in the Study Master File. The CI or designee will be responsible for the submission of annual reports and safety reports to the REC, the final REC project report / end of study notification and the prompt notification of the premature interruption of the study, should this be warranted.

8.3 Protocol compliance

Thorough training of all research staff at the study onset and subsequent weekly supervision of all research workers (e.g., assistant, therapist, ClinPsyD trainees) throughout their involvement in the study will minimise risk of deviations from protocol. However, accidental deviations from protocol can happen at any time; these will be documented and recorded in a protocol deviations log, which will be saved in the Study Master File. All deviations from protocol will be brought to the attention of the project CI, and promptly communicated to the study Sponsor, so that corrective actions could be promptly implemented. The protocol deviations log will also be reviewed at regular meetings with the experienced research team and professional steering groups for additional scrutiny and suggestions of corrective actions.

8.4 Assessment and management of risk

All digital and face-to-face contact with research participants will be conducted in accordance with bespoke standard operating procedures (SOPs) to manage any risk uncovered as part of the planned research assessments. These will comply with national and local policies for safeguarding children and vulnerable adults. In case our research assessments will uncover significant safeguarding issues or risks, participants' confidentiality may be breached to comply with safeguarding best practice and ensure the safety of all parties. This might involve disclosure of clinical and risk information to the participants' clinical teams and relevant safeguarding teams, as guided by local frameworks and policies for safeguarding children and vulnerable adults. All participants will be informed of the boundaries and limits of confidentiality at the onset of the evaluation.

The study will include the collection and discussion of sensitive topics, and some participants may find these upsetting or potentially distressing. In our experience, severe distress caused by the proposed research procedures will be highly unlikely. Nonetheless, to mitigate risk of distress, all contact with research participants will be conducted according to SOPs to manage assessments in a sensitive and respectful way. We will also follow tried-and-tested protocols for recognising and responding to potential signs of distress during and following contact with research participants. These procedures include, amongst other steps, 1) pausing of any data collection / interview procedures should a participant become distressed; 2) offering breaks and opportunities for reassurance; 3) reminding participants that their participation is voluntary and of their right to withdraw at any point, without any detriment to them; 4) procedures for signposting participants to appropriate sources of support or summon emergency services in cases of extreme risk to the participant or the public. All participants will be provided with debriefing information that will include the contact details of relevant local support services that participants could access in the event of a crisis. This debriefing document will be updated regularly to ensure that information and resources are as up to date as possible throughout the study.

All research workers contributing to data collection activities will receive regular supervision from a senior researcher within the team as well as access to line management supervision and other ad-hoc supervision and guidance from clinically qualified NHS professionals. All contacts with research participants will take place at pre-specified times agreed by project's CI or individual with delegated responsibility, and according to a 'clinical cover rota' that will guarantee that RAs within the host research centre have prompt access to clinically qualified members of the research team for initial risk management advice.

It is expected that a considerable amount of contact with research participants will be via remote means (e.g., telephone or digital platforms/software approved by the participating NHS organisations, e.g., Microsoft Teams). Risks to the physical safety of the investigator are therefore minimal in these circumstances. Any necessary face-to-face contact will be conducted in full compliance with the lone working policies of the

participating NHS Trusts and Higher Education Institutions (HEIs) where the research workers and other research workers will be based, which will include locally adapted safety checking for lone workers SOPs. Furthermore, in case of future pandemic events, any contact will be in full-compliance with all relevant COVID-19 risk mitigation policies and procedures of participating NHS organisations (or related policies/processes for other unforeseen pandemic events) and will only be conducted following approval by the CI and/or project manager following the completion of any recommended local infection control risk assessment.

8.5 Adverse event reporting and harms

Throughout the participants' involvement in the study, best practice, professional guidelines, and local NHS policies for monitoring mental state and risk for participants will be followed and will be facilitated by close liaison with clinical teams. Any adverse event (AE), clinically significant deterioration in the participants' mental state or change in risk information will be promptly communicated to responsible clinicians to ensure appropriate monitoring and provision of support.

Any AE observed over the course of the research will be documented and reported according to bespoke SOPs that will fully comply with appropriate HRA safety reporting procedures for non-CTIMP studies, Sponsor's requirements, and local R&D policies of participating NHS organisations. For example, all research contacts will be recorded in clinical notes and signed consent forms will also be uploaded/attached to clinical notes.

The occurrence of AEs will be monitored and systematically recorded by study staff. Research workers may become aware of an AE in a variety of ways, including participants' prompted or unprompted disclosure, information received from responsible clinicians, information extracted through clinical notes and usual monitoring of the participants' mental health and welfare as part of therapy sessions delivered as part of the trial. To ensure active surveillance of harms, at each followup assessment, the research workers will actively check for the occurrence of specific AEs using a structured checklist completed with the participant.

AEs are defined in line with standard HRA guidance as any untoward medical occurrence, unintended disease or injury, or untoward clinical signs in participants, whether or not related to the treatment, which require additional support or input from health professionals. Any clinically significant increase in presenting difficulties reported by participants (i.e., operationalised as an unresolved exacerbation in distress/mental health symptoms requiring increased involvement from the care team, e.g., a change in treatment plan) and reports of distress or complaints associated with therapy or other study procedure would also constitute AEs.

AE forms will be sent to the project CI (or another clinically qualified person with delegated responsibility) and assessed for:

- Severity (i.e., classified as mild, moderate, and severe according to the impact of the event on the person at the time, irrespective of whether the event also meet 'seriousness' criteria).
- Relatedness (i.e., whether the event resulted from administration of any of the research or therapy procedures, according to available information, e.g. temporal proximity to a study procedure; according to the report of the participant and the opinion of the clinical team).
- Expectedness (rated only in cases where the event is judged as related to the study procedures and intervention, and pertaining to whether the nature and severity of the observed reaction appears inconsistent with those expected from the study procedures; in the case of the JRC study, only mild and transient exacerbation in negative affect and distress are expected following a therapy session or an assessment appointment, and all other reactions will be regarded as unexpected.
- Seriousness (i.e., whether the outcome of the event meet criteria for a SAEs, including death and life-threatening events, incidents which acutely jeopardise the health or psychological well-being of the individual, events resulting in immediate hospital admission and/or persistent or significant disability or incapacity, and events resulting in injury requiring immediate medical attention, including A&E visits for mental health reasons).

Only SAEs judged to be unexpected and related to the study will be reported to the REC as per standard HRA procedures, within 15 days of the CI first becoming aware of the event. This means the REC will be notified based on the initial report, even if the final report is pending. All reportable SAEs will be reported to the Sponsor in accordance with timelines and procedures mandated by Sponsor-specific guidelines and SOPs.

All completed AE forms will be stored locally in site master files, and a central AE log will be maintained as per HRA guidance to ensure effective safety monitoring. Throughout the trial, AEs and SAEs will be regularly audited at monthly team meetings to monitor trends in AE/SAE and their implications for the ongoing delivery of the study procedures. The Sponsor and Funder will immediately be notified on receipt of any information that raises material concerns about safety of the study procedures and interventions.

Any required urgent safety measures (i.e. steps taken by the CI and/or research team in the event that there is an immediate risk to a participant or participants, without the prior approval of the NHS REC/HRA) will be notified by the CI must to the REC immediately by telephone and then follow-up with a substantial amendment within 3 days outlining the measures that have been taken and its rationale. A copy of the amendment will be submitted to the Sponsor for expedite review and sponsor authorisation of the amendment before being submitted to the NHS REC/HRA.

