Study Title	Evaluating the Implementation of a Mental Health Joint Response Car with Young People and Families
Internal ref. no. (or short title)	Mental Health Joint Response Car
Clinical Phase	Pilot and evaluation
Design	Realist synthesis Pilot and realist evaluation Health economic evaluation Co-production of iterative dissemination workstream
Study Participants	TAU - N CYP = 100 TAU - N P/C = 100 JRC - N CYP = 100 JRC - N P/C = 100 Staff - N = 20
Planned Sample Size	Children = up to 200 Parents/carers = up to 200 Staff – up to 30
Treatment duration	1 x first response call out of around 30-90 minutes
Follow up duration	Up to 6 months post contact with first response service

Planned Pilot Period	August 2024 – February 2026
Planned Study Period (Study start and end date)	1st March 2024 – 31st March 2027
Research Questions and Objectives	RQ1. What are the impacts of introducing a MHJRC for children and young people experiencing mental health crisis resulting in a 999 call? How, why, in what contexts, and for whom are these impacts generated? (Aim and Workstream 1).
	Objectives 1a. Develop theories of the underlying generative mechanisms by which, and contexts within which, a joint response between a police officer and mental health practitioner impact on mental health, options

for care, and wellbeing outcomes for young people in mental health crisis.

RQ2. What are the roles of police officers and mental health practitioners within the MHJRC model, and how do they impact young people in mental health crises? (Aims 2-3 and Workstreams 2-3).

Objectives

2a. Develop a theory to understand the roles of police officers and mental health practitioners, how they vary in different contexts across call outs, and how they impact young people across emerging adolescence, mid-adolescence, and emerging adulthood.

2b. Test and refine the theories through qualitative enquiry with young people and their families, police officers, mental health practitioners, and other connected first responders.

2c. Employ a cost-consequence approach to identify multiple effects across different sectors of the MHJRC and compare with the costs of the intervention.

RQ3. How can evidence-based theories of joint responses by police officers and mental health practitioners inform best practice guidance and support? (Aim 4 and Workstream 4).

Objective

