6.4. Taking Informed Consent

Consent for the intervention from service users.

Based on the existing NHS Standard Operating Procedure (SOP), service users provide verbal consent for an emergency response vehicle to attend during their 111/999 call. The current practice for a MHJRC joint response is that "Police Officers will enter the scene first and assess the situation prior to the mental health practitioner entering the address or interacting with the individual(s). Only when the officer deems it safe to do so will the practitioner exit the police vehicle and enter the address/location or join the responder from GMP from within the wider location if already on site (e.g., custody suite). It is appreciated that situations can however be very dynamic, and officers will respond accordingly, having due regard for the safety of the practitioner. It should be remembered that the practitioner will not be wearing a protective vest because they are not attending in the role of an emergency first responder, but of a mental health practitioner." (SOP, 2022, p.7). As the only change for our study is that the responders are attending a younger population with the specialist expertise of a CAMHS Band 7/8 practitioner, most likely a clinical psychologist, we will follow the same process as outlined in the original SOP. Once in attendance, the Police Officer and MHP will follow standard processes for risk assessment and clinical decision making, drawing upon evidence-based practices to diffuse tension and risk, providing a compassionate space to hear from the young person in crisis and other people on scene, and discuss next steps with the young person and any responsible adults present.

Consent for the evaluation from prospective participants

As per the existing SOP, "Service user's verbal consent to engage with the evaluation will be gathered on scene by the attending MHP and will be captured within clinical documentation. Following MHJRC callout, where a service user has consented to engage with the evaluation process, they will be contacted by a member of the research team and, where confirmed to be consenting once more, will engage in the evaluation." (SOP, 2022, p.15). We will follow this process for data collection at T1 (within 12 weeks of the first contact with emergency services). We will only gain consent to contact from parents/caregivers, not young people at the point of the response. Due to the distress young people and parents/carers may experience

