during mental health call outs, we propose two options for gaining informed consent for research participation in the evaluation for young people who access the Care Responders pilot.

Potential participants who hear about the study and wish to hear more will be able to contact the research team via email or phone. Once in touch, the research team will follow the assent/consent process outlined below.

Overall, informed assent and/or consent will be obtained prior to any data collection. Before the first point of data collection, participants will be provided with multiple options to confirm and document their informed consent, depending on whether contact with the research team will be face-to-face or via remote means. These will include: 1) signing a hard copy of the consent form during face-to-face meetings with research workers; 2) returning a signed hard copy of the consent form to the research team via standard mail (using a pre-paid return envelope provided by the research team); 3) returning a signed electronic copy of the consent form to the research team via email; or 4) providing audio-recorded consent (this will be recorded by research workers using an encrypted recording device and stored separately from any research data collected from study participants). The research worker will sign the consent form on behalf of the participant as instructed to do so during the consent taking process of the call. The research worker will note the consent process briefly on the consent form, alongside the date and time consent was taken.

Due to the distress young people and parents/carers may experience during mental health call outs, we propose four options for gaining informed assent/consent for research participation in the evaluation.

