6.4.1. Measures

The Strengths and Difficulties Questionnaire (SDQ; routinely employed screening and outcome measure in CAMHS) will be used at T1 and T2. The SDQ is a brief behavioural screening questionnaire for 2-17-year-olds. This single-informant measure assesses child-wellbeing and is used by clinicians at the point of referral and exit in CAMHS. Our choice of other questionnaires will be finalised by the programme theory but will likely include:

T1

Analysis of routine data sets held by GMP and PCFT (e.g. care plans, A&E admissions, acute care pathway referrals) in relation to each contact who has engagement with the MHJRC, with an additional EDI lens to evaluate whether the routine data points capture information about the context of the individual that could inform greater cultural sensitivity and accessibility. Experience of Service Questionnaire (ESQ) Child Self-report for 9–11-year-olds, ESQ Child Self-report for 12-18-year-olds, ESQ Parent/carer report

Therapeutic Experience Scale with young people, parents/carers, and staff (STAR-P and STAR-C)

KidCOPE scale 7-12, KidCOPE scale 13-18

Child and Youth Resilience Measure-Revised (CYRM, 5-9-years-old; CYRM, 10-23years-old)

Parental Stress Scale (PSS)

Session Rating Scale (SRS)

Short Mood and Feelings Questionnaire (sMFQ)

EQ-5D-Y-3L child-friendly EQ-5D version (EQ-5D-Y)

MHJRC PCFT staff will keep tabulated records of how time is spent. The study team will collaborate with members of the adult MHJRC team to develop a 'heat map' of youth and adult need/call outs across the service footprint, considering location, frequency, and key timings.

T2

Repeat ESQ, KidCOPE, CYRM-R, PSS.

These measures will address the research questions by gathering data on the impact of the MHJRC on wellbeing, service experience, therapeutic nature of relationships,

coping ability over time, and stress. This data will be enriched through the collection and analysis of qualitative data from the interviews.

!			
 			
1			

Time point / Participant group	In person/video call T1 (within 12 weeks of engagement with MHJRC/TAU)	In person/ video call T2 (3-month follow-up)	In person/ video call T2 (6- month follow-up)	Qualtrics Survey T1 Route 1: within 12 weeks of engagement with MHJRC/TAU Route 2: Within two years	Qualtrics Survey T2 (Only if Route 1: T1 was within 12 weeks of engagement with MHJRC/TAU)

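### Section 8.5 places the only structured adverse-event check at follow-up, about 13 to 38 weeks after a one-off call-out, and its causality rules refer to therapy that the study does not deliver

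*Protocol*

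**What the plan says.** The Project summary describes the treatment as "1 x first response call out of around 30-90 minutes" and the follow-up duration as "Up to 6 months post contact with first response service". Under 6.4 Taking Informed Consent, "informed assent and/or consent will be obtained prior to any data collection", and for T1 the Protocol states: "We will follow this process for data collection at T1 (within 12 weeks of the first contact with emergency services". The same section calls T1 the baseline.

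Section 8.5 sets the active check: "at each followup assessment, the research workers will actively check for the occurrence of specific AEs using a structured checklist completed with the participant". The end of 6.5 says much the same, placing active checking in the follow-up period. Section 8.5 also lists other ways in which an AE may come to light: prompted or unprompted disclosure, responsible clinicians, clinical notes, and monitoring during therapy sessions.

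For classification, 8.5 judges relatedness by whether the event arose from research or therapy procedures. On expectedness it says that "only mild and transient exacerbation in negative affect and distress are expected following a therapy session or an assessment appointment"; every other reaction counts as unexpected. Only serious AEs that are both related and unexpected go to the research ethics committee.

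Separately, 6.4.1 plans an analysis of routine police and Trust data, including A&E admissions and acute referrals, "in relation to each contact who has engagement with the MHJRC".

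**The concern.** With a one-off intervention, the period of most interest for harm begins when the responders leave. An active check that first takes place at follow-up puts the only systematic question months after that period and relies on recall. It also depends on the participant still being in the study and on the study still collecting data.

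The second problem concerns classification. If relatedness is tested against therapy and research procedures only, an event caused by the call-out has no clear route to being called related. Expectedness is rated only for events already judged related, so the relatedness rule is the first gate to external reporting.

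The Protocol's first aim covers negative as well as positive impacts (2.1), and section 1.1 asserts that the intervention should carry less risk than standard practice. Safety capture should be able to bear on both.

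**Working it through.** **Timing of the first active check.** The inputs are:

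- T1 at 0 to 12 weeks after contact (6.4 Taking Informed Consent).
- A 6-month follow-up (6.4 Data Collection), and also a 3-month column in the 6.4.1 schedule. Both are labelled T2.
- 3 months taken as 13 weeks and 6 months as 26 weeks.
- Intervention ending by 31 January 2026 and data collection by 31 March 2026 (section 7).

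Weeks to first check = weeks to T1 + follow-up interval. If the interval is counted from contact, it is the follow-up interval alone. The latest call-out that can still be checked is 31 March 2026 minus that number of weeks.

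| Case | Weeks from call-out to first active check | Latest call-out that reaches it by 31 March 2026 |
|---|---|---|
| 3-month visit, T1 immediate or interval counted from contact | 0 + 13 = 13 | 30 December 2025 |
| 3-month visit counted from T1, T1 at week 12 | 12 + 13 = 25 | 7 October 2025 |
| 6-month visit, T1 immediate or interval counted from contact | 0 + 26 = 26 | 30 September 2025 |
| 6-month visit counted from T1, T1 at week 12 | 12 + 26 = 38 | 8 July 2025 |

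The Protocol does not settle which row applies. The Project summary counts follow-up from contact, the summary of pathways in 6.1 describes T2 as six months after T1, and the schedule carries both columns. In every row the last checkable call-out comes before the intervention ends. If only the 6-month visit is held, call-outs from October 2025 to January 2026 (four months) cannot reach it even on the shorter count. For those families T1 is the only research assessment they can have, and it carries no stated checklist.

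**What is scheduled at T1.** The assessment schedule in 6.4.1 lists no AE checklist in any column, including T1 in person and Qualtrics T1 and T2. Read with 8.5 and 6.5, nothing states that the checklist is used at T1.

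**Classification rules against the intervention.**

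| Element | Where | What it refers to |
|---|---|---|
| Treatment | Project summary | One call-out, no course of therapy |
| Detection | 8.5 | Includes monitoring in therapy sessions |
| Relatedness | 8.5 | Research or therapy procedures; call-out not named |
| Expectedness | 8.5 | First mentions study procedures and intervention, then defines what is expected after a therapy session or assessment appointment |
| Report to ethics committee | 8.5 | Serious, related and unexpected |

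Therapy sessions appear again in 8.6, in connection with recordings, but no section schedules any. The relatedness and expectedness bullets also differ from each other, since only the second mentions the intervention.

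**Who is covered.** Section 8.5 concerns participants, and consent precedes any data collection. Young people who receive the call-out but do not join the evaluation are therefore outside AE reporting. The routine data in 6.4.1 do cover each contact, but no section links them to the AE log or to review of serious events.

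**The case against.** The strongest case against the point is that the Protocol has other ways of seeing harm. Disclosure, clinicians and clinical notes are stated AE routes that are not tied to a follow-up visit, and clinical notes can cover the days after the call-out. T1 includes mood and difficulties questionnaires and an interview on subsequent wellbeing, and 6.8 sets out a safeguarding plan at T1 and T2. The checklist's recall period is not stated and the AE procedures sit in SOPs not shown here, so a follow-up checklist might ask back to the call-out. Section 8.5 also escalates material safety concerns about the intervention, and it treats everything beyond mild, transient distress as unexpected, which is conservative.

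Much of this stands, and it rules out several stronger readings:

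- A reader might infer that harms from the intervention go largely unseen. The passive routes and the routine data on each contact contradict that.
- A reader might put a percentage on the uncovered weeks or on the non-consenters. Twelve weeks is a maximum, the start of the follow-up clock is unsettled, and no consent rate is given.
- A reader might conclude that online participants never meet a researcher. The Protocol removes that contact only at initial data collection. It invites online participants who are within 12 weeks of the crisis to interviews at T1 and T2, and it allows guided completion by email.
- A reader might expect families with a bad outcome to be the least likely to enrol. The documents offer no evidence either way, and they provide a later call and a 12-week opt-in.
- Serious events are defined as "including A&E visits for mental health reasons", among others, and A&E attendance is also an outcome. A reader might infer that the result of the index call would be logged as a serious event. AEs are defined in participants, and the call-out comes before consent, so this is not shown.

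None of this supplies a structured check at T1, helps late call-outs that never reach follow-up, or brings the call-out within the relatedness rule.

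**Conclusion.** The point holds as a defect in the timing and wording of safety capture. The first structured AE check comes about 13 to 38 weeks after the call-out, and may not occur at all for call-outs late in the pilot. Until then, capture as an AE is passive. The relatedness and expectedness rules do not fit the intervention described in the Project summary, although they govern what is reported to the ethics committee. Relatedness matters more, because the expectedness rule is already conservative.

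The range assumes 13 and 26 weeks for the two follow-up intervals and T1 anywhere from 0 to 12 weeks. It concerns people enrolled within 12 weeks of the crisis; participants reporting on past usual care may be up to two years from the event. If the unseen SOPs make the checklist ask back to the call-out, the gap for those who reach follow-up becomes one of delay and recall. The late call-outs and the wording would be unaffected. The documents do not support saying that harm is mostly missed.

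**What to change.** 1. In 8.5 and the 6.4.1 schedule, state that the structured AE checklist is used at T1 as well as at each follow-up, and that at T1 it asks back to the index call-out. Include the same items in the Qualtrics T1 and T2 surveys.
2. Reconcile the therapy wording in 8.5 with the treatment described in the Project summary, so that relatedness and expectedness both cover the call-out. Also reconcile the 3-month and 6-month columns labelled T2 with the text, so that the timing of the follow-up check is defined.
3. Tabulate adverse outcomes from the routine police and Trust data already planned for each contact, and present them beside the AE log. This covers, in aggregate, contacts who do not join the evaluation.

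The cost is a short amendment, a few extra items at T1 and in the surveys, and one extra table. A matching table for usual care over fixed short windows is not required. The routine extract in 6.4.1 is described for joint response contacts, so such a table would be new data work.
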